#### **7.3. Informed Consent**

Patients who complete the LCS eligibility survey and meet the study eligibility criteria will be then contacted via phone by a study coordinator speaking the patients' language for a study overview and consenting. A signed and dated written informed consent form (ICF) will be obtained from the patient via DocuSign, fax or mail. A signed copy of each ICF will be given to the patient or they can download it via REDCap.

#### 7.4. Screening Confirmation

Patient information should be entered into OnCore within 5 business day of consent. Each site is responsible for assigning subject ID.

#### 7.5. Baseline Survey

Patients will be asked to complete a 15-min survey either on the phone or online via REDCap based on preference. This survey includes validated measures utilizing the Health Belief Model to assess perceived risk of getting lung cancer, benefits and barriers to LCS, and self-efficacy for LCS, prior receipt of any screening exam, overall willingness to undergo LCS with LDCT, and engage in receiving LCS educational information. We will further screen for health-related social risks such as financial hardship, difficulties in paying for food, transportation, and housing instability as a barrier to receipt of LCS, and query on demographics, insurance, health literacy, zip code (to assess neighborhood socioeconomic status), and presence of other comorbidities and healthy behaviors. Participants with completed survey will be sent a \$15 gift card. Survey materials will be available in English, Spanish, and Vietnamese.

#### 7.6. Study Intervention

Consented patients completing baseline survey will receive usual care which includes a provider flag in EMR on their eligibility for LCS if their smoking history is complete.

Our intervention includes:

(1) Primary Care Provider notification of patients' LCS eligibility, and their self-reported barriers to receipt of LCS based on baseline survey. The notification will be sent using an EPIC secure message and via email within 2 weeks prior to scheduled PCP visit. If a patient cancels or reschedules the appointment, the message will still be sent within 2 weeks of the initial appointment. Prior to study activation, all UCI PCPs will be emailed and notified of our study.

For non-UCI Health PCPs, reminders to discuss LCS will be sent via secure email or direct phone calls to their office. Non-UCI Health PCPs will not directly engage in research activities and will instead continue to administer standard patient care. Non-UCI Health PCPs will not represent the study.

(2) patient education of LCS: patients will be mailed (paper) and emailed (PDF from; if have an email address) information (in preferred language) on lung cancer risk, LCS benefits, harms, false positive rates, recommendations of follow-up for positive results, and exam insurance coverage. Publicly available resource "Should I Screen" and baseline survey data will be used to create material.

(3) patients' referral to financial navigation resources: Patients who self-report needing help with health-related social risks at baseline will be mailed (paper) and emailed (PDF

from; if have an email address) a brochure (in preferred language) from patient advocate foundation (PAF), a national non-profit financial navigation organization, where patients can self-refer;

(4) patients' reminder to discuss LCS during PCP visit: within 2 weeks prior to appointment, all patients, regardless of their site for care, will receive a text message or a phone call (if not having a phone that receives text messaging) encouraging patients to discuss the LCS with their provider.

## 7.7. Patient Follow-up

Patients will be surveyed 6 months after enrollment to assess self-reported LCS discussion with PCP, provider order of LDCT, and patients' receipt of LDCT. We will also extract these from EMR only for UC-Health patients. Patients will be queried on LCS perceived risks, benefits, barriers, and self-efficacy, experience with intervention including educational material, reminders, and self-referral to PAF if PAF brochure was received.

Surveys will be completed online (REDCap), on the phone or paper (mailed with a pre-stamped pre-addressed envelope) based on patient's preference. Patients with completed survey will receive a \$15 gift card.

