### **10.4. Statistical Analyses**

We will work with the Biostatistical Shared Resource, and report proportion of LDCT order, receipt of LDCT, and LCS discussion using descriptive measures. We will compare pre-post measures of perceived risk to lung cancer, LCS benefits, barriers, and self-efficacy using paired t-tests or Chi-squared tests, where appropriate. Multivariable regression analyses will be performed adjusting for covariates. We will report rate concordance of EMR and self-reported smoking history. Qualitative interviews will be translated and transcribed verbatim, and they will be reviewed and discussed iteratively using a “theoretically-driven thematic analysis” approach. The coding sequence will be conducted on a line-by-line unit of analysis using the Dedoose online system. We will use deductive and inductive approaches, organizing the data according to the domains in the interview guide and then open code the transcripts and inductively search for specific patterns and themes in each domain. We will develop the codebook based on the domains, emergent themes, and discussion. Coders will independently (and then collectively) examine and assemble coded data to identify themes within categories and relationships among them.

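### Survey mode is chosen afresh at baseline and at 6 months and is left out of the analysis, so net switching between phone and self-completion would enter the paired belief change

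*Combined protocol and SAP*

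**What the plan says.** **Baseline (Section 7.5).** "Patients will be asked to complete a 15-min survey either on the phone or online via REDCap based on preference". Paper is not offered. The survey includes items "to assess perceived risk of getting lung cancer, benefits and barriers to LCS, and self-efficacy for LCS".

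**Six months (Section 7.7).** "Surveys will be completed online (REDCap), on the phone or paper", with paper sent by mail and the choice again left to the patient. The same domains are asked again: "Patients will be queried on LCS perceived risks, benefits, barriers, and self-efficacy".

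**Analysis (Section 10.4).** "We will compare pre-post measures of perceived risk to lung cancer, LCS benefits, barriers, and self-efficacy using paired t-tests"; the sentence goes on to allow chi-squared tests where those fit better. For the screening outcomes the plan is to "report proportion of LDCT order, receipt of LDCT, and LCS discussion using descriptive measures", with no test. Multivariable regression is also planned, but no outcome or hypothesis is named for it.

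**Design and covariates.** Section 5.2 describes a single-arm study of 70 patients. The covariates in Table 2 do not include survey mode. No section says that mode will be kept the same within a patient, recorded as an analysis variable, or adjusted for.

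Section 7.1 does mention mailed surveys, but as part of recruitment and eligibility outreach. They do not supply a paper version of the baseline survey.

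**The concern.** A paired change in an uncontrolled study can be read as change in the patient only if the measurement is made the same way both times. Here each patient picks a mode twice, independently, and the menu is longer the second time. Answers given aloud on the phone may differ from answers given alone on items such as perceived barriers or self-efficacy. That is a general measurement concern; the documents say nothing about it for these scales.

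When a patient changes between phone and self-completion, any such difference goes into that patient's change score. No control arm shares the shift and subtracts it, and no term in the analysis absorbs it. At stake is the reading of the belief results: a shift produced by the way the questions were asked could be reported as a change in beliefs after the intervention. If mode is not recorded when each survey is completed, it may be impossible to tell afterwards.

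**Working it through.** The plan gives no figure to reproduce. Section 10.1 justifies 70 patients by feasibility, without an alpha, power, effect size, SD or dropout rate. What follows is an illustration.

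**Inputs**
- n = 70 pairs: Section 5.2, taken as all completing.
- Two-sided 5% test: assumed.
- SD of change equal to the baseline SD: assumed. Since SD of change = sqrt(2(1 − rho)) in baseline SD units, this is a pre-post correlation rho of 0.5.
- f, the net share switching: the share moving one way between phone and self-completion, minus the share moving the other way. Assumed 0.2 to 0.4. Online to paper counts as no switch, because both are self-completed.
- d, the mode effect in baseline SDs: assumed 0.2 to 0.3.
- No true change in beliefs.

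**Formulas**
- SE = 1/sqrt(70) = 0.12 SD.
- Bias in the mean change = f × d.
- Rejection rate = P(|Z + bias/SE| > 1.96).

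**Results**
- Low end: bias = 0.2 × 0.2 = 0.04 SD, or about 0.3 SE. Rejection rate 6.3%.
- High end: bias = 0.4 × 0.3 = 0.12 SD, or about 1.0 SE. Rejection rate 17.1%.
- f = 0: bias 0, rejection rate 5%.

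**Second check.** This uses the noncentral t distribution, with SD of change = sqrt(2(1 − rho) + f(1 − f)d²) and rho from 0.5 to 0.7, both assumed. The false-positive rate per scale at n = 70 is:

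| Net switching | d = 0.2 | d = 0.3 |
|---|---|---|
| 10% | 5.3–5.5% | 5.7–6.2% |
| 20% | 6.2–7.1% | 7.8–9.7% |
| 30% | 7.8–9.7% | 11.4–15.7% |
| 50% | 13.0–18.4% | 23.2–34.8% |

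In each cell the higher figure belongs to rho = 0.7, because a smaller SD of change makes the same bias weigh more. With 56 pairs (an assumed 20% loss), 30% net switching and d = 0.3, the rate is 10.1–13.4%. At n = 70 an observed mean change of about 0.19 to 0.24 SD is enough for p < 0.05, so a bias of 0.04 to 0.12 SD is a modest to appreciable part of that threshold.

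**The case against.** The strongest reply is that the argument needs net switching, and the documents give no reason to expect much. Phone and online are available both times and the same person chooses, so many patients may simply repeat their choice. Moves in opposite directions cancel in the mean. Online to paper is self-completion both times, so the added paper option matters only for patients who were on the phone at baseline. The switching share and the mode effect are both assumed. This point stands: the direction is unknown and the size could be close to nothing.

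A second reply is that the stakes are limited. This is a feasibility study, the plan sets no alpha or success threshold for the belief scales, and no decision hangs on their p-values. LDCT order is measured at 6 months only and reported descriptively. This also stands, and it holds the importance down. Other threats to an uncontrolled pre-post change, such as time trends, repeat testing, regression to the mean and dropout, remain whatever is done about mode. Mode differs from most of them in that the study team can control it directly.

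A reader might go further and infer that late responders will be pursued by phone, which would push switching in one direction. The documents do not support that. Section 7.7 describes no such follow-up and says only that mode follows the patient's preference. Phone contact with people who do not answer appears in Section 7.1, for recruitment. A drift towards phone would also run against a drift from phone to paper, so a one-way bias cannot be presumed.

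**Conclusion.** The gap is real. Mode is chosen separately at the two surveys, is not held constant, and is absent from the analysis of the plan's only named significance test. Net movement between phone and self-completion would bias the mean belief change. On the stated assumptions the nominal 5% test would reject in about 6% to 17% of studies with no true change; with little or no net switching the inflation is negligible. Of the inputs, only the sample size comes from the documents.

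Two stronger readings should be avoided. The belief comparison is the only named significance test, but not the only planned inference, because Section 10.4 also mentions a regression with no stated outcome. And the primary endpoint is not compromised by this test. The point is a cheap improvement of low-to-moderate importance.

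**What to change.** **Section 7.7:** offer each patient the baseline mode first at 6 months. Keep the other modes, including paper, as fallback so that response is protected.

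**Sections 7.5 and 7.7:** record the mode used at each survey, at the time of completion.

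**Section 10.4:** add a sensitivity analysis of the belief change, either by mode pattern (phone versus self-completed, same versus switched) or with a mode-change term. State that the same-mode subset is smaller and is selected on behaviour after baseline, so it may differ from the full sample for reasons other than mode. It is a check on the main result and should not replace it.

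The cost is a sentence of survey procedure, one recorded field per survey and a line of analysis.

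Adding paper at baseline would make the two menus match, but it is not recommended. Table 1 places the baseline survey before the intervention and the primary care visit, and under Section 7.6 its answers feed the provider notification sent in the two weeks before that visit. Postal return would have to fit inside that sequence.

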## 7.8. Non-patient participant Follow-up

Any of the UCI Primary Care providers who receive a provider notification of their patients' LCS eligibility as part of the study will be eligible to participate. Three months after last patient enrollment, we will send an electronic REDCap information sheet to all eligible providers and ask them to complete an online 10-minute survey.

The survey includes questions pertaining to provider demographics, clinical practice, perception regarding barriers to LCS, awareness of CMS beneficiary eligibility criteria for LDCT using a validated questionnaire, providers' experience with EMR flags they receive for patients' LCS eligibility as part of usual care, as well as their experience with the patient-specific LCS eligibility notification they received as part of the study and whether that prompted them having a LCS discussion with their patients. Additionally, we will inquire about their interest in future development of a provider-directed educational material. Survey participants will receive a \$15 gift card. We expect 20-40 providers participate in the survey.

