## 1. PROTOCOL SYNOPSIS

Study Number	UCI 23-107
Study Title	Empowering patients' Lung Cancer Screening uptake (Empower LCS)
Development Phase	II
Funding Source(s)	Anti-Cancer Challenge Pilot Award
Operational Changes during the COVID-19 Pandemic	N/A
Sources of Study Drugs	N/A
Number and Identity of Study Sites	University of California Irvine Health
Study Rationale	Utilization of lung cancer screening (LCS) using Low Dose CT (LDCT) among those eligible is low. We are assessing feasibility of a multi-level intervention to improve lung cancer screening uptake.
Study Design	Single arm longitudinal study
Study Objectives	
 
1. Assess feasibility of our multi-level intervention in increasing patients' LCS knowledge, having a LDCT ordered, and patients' receipt of LCS with LDCT.
 
2. Assess LCS-eligible patients' and their providers' perceptions and barriers towards LCS.
 
3. Describe patients' & providers' experience with the intervention using a mixed-methods approach.
 

Planned and Maximum Sample Size	70 patient participants (English, Spanish, and Vietnamese speaking), and between 20-40 non-patient participants.
Duration of Study Participation	
Patient participants: 6 months. Up to 15 patients will be asked to participate in a 30-min interview after 6 months completion of the study.
 
Non-patient participants: One time. 5 non-patient participants will be asked to participate in a 30-min interview within 3 months of last patient enrollment.

Indication(s) Under Study	Patients eligible for lung cancer screening
Inclusion Criteria	
 
1. Aged 50- 80 years of age.
 

	
 
2. Be able to Speak English, Spanish, or Vietnamese
 
3. Must have a primary care provider
 
4. Meeting the LCS eligibility criteria based on self-reported smoking history (for UCI and non-UCI Health patients) as well as documented in EMR (for UCI Health patients) and confirmed prior to enrollment
 

Exclusion Criteria	
 
1. No prior history of lung cancer
 
2. No chest CT for any reason in the last 12 months based on self-report (for UCI and non-UCI Health patients) and UCI EMR (for UCI Health patients)
 
3. No history of Alzheimer's disease or dementia
 

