**Table 1 Schedule of Events**

	Pre-Screen	Screen	Baseline	Primary Care Appointment	6 months Follow-up	Provider Survey	Interview
UCI Health IT inquiry	X						
Distribution of flyer to community clinics and Spanish and Vietnamese speaking social media and news outlet	X						
Screening 2-min survey		X					
Informed Consent			Prior to PCP appointment				
Baseline Survey			After informed consent prior to PCP appointment				
Intervention delivery				After baseline survey, prior to PCP appointment			
Follow-up survey					Within -14 and +30 days of 6 months follow-up		
Provider Survey						Within 3 months of last patient enrollment	
Interview							Within 30 days of patient or provider completion of their survey.

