##### 5.2. Overall Study Design

We will conduct a single arm longitudinal clinical trial of 70 LCS-eligible patients with a PCP appointment at UCI health within five **months** after enrollment. All patients will complete a baseline survey to assess their perceptions and barriers towards LCS and will receive a multi-level intervention. All patients will complete a survey at 6 months post-enrollment to assess changes in perceptions and knowledge, receipt of an order for LDCT or completion of LDCT, and experience with intervention. All primary care providers of enrolled patients will be sent a survey 3 months after last patient enrollment to assess providers' barriers to order LCS. We will interview randomly selected up to 15 patients and 5 PCP participants with highest enrolled patients in the study, who consent to be interviewed to assess experience with the intervention.

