## 8. EFFICACY ASSESSMENTS

Primary end point is order of LDCT within 6 months after enrollment assessed with self-reported surveys (for UCI-Health and non-UCI health patients) and EMR data extraction (for non-UCI Health patients). Remainder of outcomes is show in Table 2.

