**Table 2 . Study Outcomes, Measures and co-variates**

Efficacy Outcomes		
LDCT order for LCS	6 mo	Survey and EMR
Receipt of LDCT for LCS	6 mo	Survey &EMR
Pt and PCP LCS discussion	6 mo	
Pt perceived risks, benefit, barriers, and self-efficacy using LCS health belief mode 	Baseline & 6 mo	Survey
Process Evaluation Outcomes		
Rate of concordance of EMR and self-report smoking hx	Baseline	Survey& EMR
Showing up to PCP visit	6 mo	
Self-referral to PAF	6 mo	Survey
Pt and provider experience with intervention components	6 mo	Survey& interview
Provider perceived barriers and knowledge of LCS	Beginning 9 mo after first pt enrollment	Survey
Covariates		
Sociodemographics, insurance, neighborhood deprivation index, health literacy, comorbidities	Baseline	Survey
Financial worry  and health-related social risks 	Baseline & 6mo	Survey

- Any mention of ER is only for UCI Health patients.

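### UCI primary care providers are surveyed and interviewed about lung cancer screening while some late-enrolled UCI patients are still in their 6-month LDCT-order window, so this contact can prompt orders that the single-arm proportion cannot separate from the intervention

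*Combined protocol and SAP*

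**What the plan says.** **Endpoint.** Section 8: "Primary end point is order of LDCT within 6 months after enrollment". The clock starts at each patient's own enrollment. Section 5.2 describes patients "with a PCP appointment at UCI health within five" months of enrollment, so the index visit can fall as late as month 5. Section 7.6 sends the provider notification within 2 weeks before that visit.

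**Provider survey.** Its timing is given in four places:

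- Section 5.2: providers "will be sent a survey 3 months after last patient enrollment".
- Section 7.8: "Three months after last patient enrollment, we will send an electronic REDCap information sheet to all eligible providers".
- Table 1: "Within 3 months of last patient enrollment".
- Table 2: "Beginning 9 mo after first pt enrollment".

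Section 7.8 limits the survey to UCI providers who received a study notification. It covers barriers to screening, awareness of LDCT eligibility criteria, the usual-care EMR flags and the study notification, including "whether that prompted them having a LCS discussion with their patients".

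**Provider interviews.** The Synopsis says: "5 non-patient participants will be asked to participate in a 30-min interview within 3 months of last patient enrollment". Table 1 instead places interviews within 30 days of the provider's own survey. Section 7.9 selects the five providers with the most enrolled patients and asks them about barriers to ordering.

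**Analysis.** Section 10.4 reports the LDCT-order proportion descriptively, in one arm. Nothing in the protocol delays provider contact until windows close, or flags orders placed after it.

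**The concern.** The primary care provider controls the primary endpoint. A questionnaire or interview on why screening is not ordered, who qualifies for LDCT, and whether the study message led to a discussion is a plausible cue to order. It is not among the four components in section 7.6, and it can act only on UCI patients enrolled late enough to be in window.

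Without a control arm, an order that follows this contact looks the same as one that follows the notification, the education, the financial referral or the patient reminder. At stake is what the reported proportion describes: the four-component intervention, or that intervention plus a research contact that would not be carried forward. The same applies to the outcome of patient-provider screening discussion at 6 months.

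**Working it through.** The protocol states no power calculation (section 10.1 justifies 70 patients by feasibility) and no overlap figure, so there is nothing of the plan's own to reproduce. The check is calendar arithmetic.

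**Inputs.** N = 70 (sections 5.2, 5.4 and 10.1). Window = 6 months from enrollment (section 8). Survey at L + 3 months, where L is the last enrollment (sections 5.2 and 7.8), or anywhere from L to L + 3 as I read Table 1. Interview by L + 3 (Synopsis), or up to 30 days after the survey, so about L + 4 after a survey at L + 3 (Table 1). Accrual length A is not stated. I assume uniform accrual and show a range.

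**Formula.** A patient enrolled x months before L has a window closing at L − x + 6. Contact at L + s falls inside it when x < 6 − s. The share in window is min(1, (6 − s)/A).

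| Contact at | A = 6 | A = 9 | A = 12 | A = 18 |
|---|---|---|---|---|
| L + 0 (earliest under Table 1) | 100% (70) | 67% (46.7) | 50% (35) | 33% (23.3) |
| L + 3 (5.2, 7.8) | 50% (35) | 33% (23.3) | 25% (17.5) | 17% (11.7) |
| L + 4 (interview after that survey) | 33% (23.3) | 22% (15.6) | 17% (11.7) | 11% (7.8) |
| L + 6 | 0 | 0 | 0 | 0 |

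At L + 3, the patients still in window have between 0 and 3 months left, 1.5 on average.

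These counts are upper bounds on exposure. They use all 70 patients, whereas non-UCI patients, patients with an order already placed, and patients whose provider does not respond are not exposed.

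**Index visit still to come.** If visits are also uniform over months 0 to 5, a patient enrolled x months before L has probability (2 − x)/5 of a visit after the L + 3 survey, for x < 2. The integral from 0 to 2 is 0.4 month. Dividing by A gives 0.4/6 = 6.7%, 0.4/9 = 4.4% and 0.4/12 = 3.3%, or about 4.7, 3.1 and 2.3 of 70 patients.

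**Table 2.** Its start date matches L + 3 only if 9 = A + 3, that is, A = 6. The last window closes A + 6 months after first enrollment, so a start at month 9 precedes that close whenever A > 3. If A > 9, the survey could begin before enrollment ends. Choosing among the existing statements therefore does not remove the overlap, unless Table 2 governs and accrual takes 3 months or less.

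**Illustrative effect.** Suppose contact raised the order probability of every in-window patient by 5 to 20 points (an assumption; the documents give no figure). The overall proportion would then rise by at most (3/A) times that amount: 2.5 to 10 points for A = 6, 1.25 to 5 for A = 12, and 0.8 to 3.3 for A = 18. For scale, the 95% half-width 1.96 × √(p(1 − p)/70) is 7.8, 10.7 and 11.7 points at p = 0.128, 0.30 and 0.50.

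**The case against.** A reader might infer that the survey does inflate the primary endpoint. The documents do not support that; they show an opportunity, not an effect. Every surveyed provider has already had at least one study notification, all UCI providers are emailed about the study before activation, and usual care includes an EMR flag when smoking history is complete. The survey items concern general barriers and past experience, and none is described as naming patients still due for an order. The increment over a patient-specific message may be small. This stands.

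A reader might also infer that every patient enrolled in the last 3 months is exposed. That is not so: only notified UCI providers are surveyed, and non-UCI providers take no part in research activities. Only the five provider interviews are at issue, because patient interviews follow the 6-month follow-up. This stands too.

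A further tempting inference is that the provider-experience objective is answered before providers have had the exposure. Survey eligibility requires a notification already received, so respondents have something to report. What remains is minor: a few late notifications may be missed.

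Finally, this is a feasibility pilot with no test or success threshold, and an earlier survey shortens recall. Both points are fair. They limit the consequence but do not remove the overlap, and the overlap is cheap to avoid.

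**Conclusion.** The overlap holds under every provider-contact time anchored to last enrollment. While some late-enrolled UCI patients are still in the LDCT-order window, their providers are contacted about screening and ordering outside the four intervention components. This can prompt orders or discussions, and the single-arm proportion cannot separate them out.

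At the L + 3 survey, the in-window share is at most 50%, 33% or 25% for 6, 9 or 12 months of accrual. This rests on assumed uniform accrual and an accrual length the protocol does not give. It measures opportunity, not bias; the bias cannot be computed from the documents and may be small. The point is a worthwhile, low-cost improvement and does not invalidate the endpoint.

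**What to change.** **Preferred.** Reconcile the timing statements in the Synopsis, section 5.2, section 7.8, Table 1 and Table 2. Send provider surveys and hold provider interviews only after the last enrolled patient has passed the 6-month date. Alternatively, once enrollment has closed, trigger each provider's contact when that provider's own last enrolled patient has passed it. With contact at L + 6 or later, no patient is in window.

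The cost is protocol wording and a REDCap trigger date, plus about 3 months' longer recall of early notifications. The change fits within existing follow-up, since Table 1 already lets the last patient's survey run to 6 months plus 30 days.

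**If the timing stays.** Record the date each provider was first sent the survey or interviewed. Using EMR order dates for UCI patients, report the LDCT-order proportion again without orders placed after that provider's first contact. Label it a lower bound, because it also drops orders that the intervention itself produced at later visits. The cost is one date field and one extra descriptive line. Section 8 assigns EMR extraction to non-UCI patients, whereas the Synopsis, section 7.7 and the Table 2 footnote assign it to UCI patients. Correct this at the same time, because the sensitivity analysis depends on it.
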